8.7.2 Reporting of Serious and Unexpected Suspected Adverse Reactions (SUSARS)

A serious suspected adverse reaction is any serious adverse event for which there is a reasonable possibility that the study drug caused the adverse event. A serious adverse reaction is considered "unexpected" (serious and unexpected suspected adverse reaction; SUSAR) if it is not listed in the APP13007 Investigator's Brochure or is not listed at the specificity or severity that has been observed.

SUSARs with an outcome of death or are life threatening must be reported to the relevant Regulatory Authorities within 7 calendar days, all other SUSARs must be submitted within 15 calendar days. The SUSAR reporting procedures are detailed in the study Safety Management Plan. This plan is an agreement between the Sponsor, the CRO for Study Management and Monitoring and Synergy Research Pharmacovigilance.

NOTE: The Sponsor will notify the U.S. Food and Drug Administration (FDA) and all participating site Investigators of any SUSARs (via the CRO for Study Management and Monitoring) on an expedited basis and in accordance with applicable regulations. In addition the sponsor is responsible for informing all Investigators in all ongoing studies involving the study drug about all SUSARs.

Medical and administrative data related to Individual Case Safety Reports which qualify for expedited and periodic reporting, should be provided in compliance with U.S. FDA Code of Federal Regulations (CFR) 21, 312.32.

It is the responsibility of the Investigator to promptly notify the IRB and other appropriate institutional regulatory bodies of all unexpected serious adverse reactions involving risk to human subjects as per their applicable requirements.

9.0 SAFETY MANAGEMENT

9.1 Stopping Criteria

9.1.1 Individual Subject

9.1.1.1 Lack of Efficacy (See [Section 9.4](#))

The Investigator should consider whether to stop the study drug because of lack of efficacy and rescue the subject with alternative therapy (see [Section 9.4](#)).

Rescued subjects shall continue in the study and be assessed at each subsequent scheduled visit until Visit 6 (POD22). The study drug will be stopped as indicated in [Section 9.4.2](#).

9.1.1.2 Elevated Intraocular Pressure (See [Section 9.5](#))

The Investigator should consider whether to stop the study drug because of an elevation of IOP. The study drug may or may not be continued as indicated in [Section 9.5.2](#).

9.1.1.3 Deleterious Effects of the Study Drug

The investigator may stop the study drug and withdraw the subject if in their opinion the study drug is having a deleterious effect on the subject's health or wellbeing. The investigator should make an effort to follow up the subject until the deleterious effect is resolved.

9.1.1.4 Lack of Compliance

The investigator may stop the study drug and withdraw the subject if in their opinion the subject is not complying with study procedures, including, but not limited to, dosing of the study drug.

9.1.2 Study Termination

- The study can be stopped at any time if deemed necessary by the Sponsor Medical Monitor, in consultation with the Study Medical Monitor, due to safety concerns. Safety will be monitored on an ongoing basis via periodic masked review of AEs and other safety endpoints.
 - If it is observed that visual acuity worsens by 2 lines (Base LogMAR change of 0.2 using ETDRS chart) at Visit 6 (POD22) in the treated study eye as compared to Visit 2 (POD1), in 6 consecutive subjects, no further doses of study drug will be administered to any subjects in the study until a comprehensive evaluation can be performed, and, if possible, a cause is identified.
- Safety assessments will be performed throughout the course of the study. The APP13007 Investigator's Brochure, Section [1.4.1](#) and the Risk Mitigation plan in [Table 2](#) provide guidance for the Investigator on potential anticipated AEs that may occur. Any potential

important safety issues that arise will be reviewed by the Study Medical Monitor, in consultation with the Sponsor Medical Monitor, to identify the appropriate course of action.

- If the Sponsor elects to terminate the study for any reason, the Investigator will be responsible for notification of the IRB and will withhold further dosing of study drug.

9.2 Dose Modification

No dose modification is permitted.

All instances of missed doses must be recorded.

Note: Study drug bottle will be replaced if a bottle is lost or otherwise compromised before Visit 5 (POD15) (see [Section 5.1.2](#)).

9.3 Dosing Interruptions

Investigator is not allowed to modify the dosing regimen due to an AE or any other circumstance, but the Investigator has the option of stopping study drug after consultation with the Study Medical Monitor, if feasible.

Subjects will be permitted to restart study drug if there is a temporary dosing interruption of study drug of not more than 1 day due to an AE.

9.4 Rescue Management

9.4.1 Criteria for Starting Rescue Medication

Any subject not responding to the study drug because of lack of efficacy at any time after randomization at Visit 2 (POD1) may be rescued and placed on an appropriate alternative therapy determined by the Investigator.

In general, at any visit, a subject with worsening inflammation or showing no improvement in degree of inflammation compared with the previous visit is eligible for rescue therapy at the discretion of the Investigator. However, the following guidance is provided to Investigators for consistency in the way subjects are rescued:

1. Subjects who, on examination of the anterior chamber, have one or more of the following quantitative criteria should be rescued and discontinued from study drug dosing and placed on rescue mediation:
 - An increase of ACC count by > 15 cells from the Visit 2 (POD1) pre-dose baseline.
 - A ≥ 2 grade increase in ACF grade from the Visit 2 (POD1) pre-dose baseline.

2. Subjects who have the following qualitative criteria may be rescued. If the subject is rescued, the study drug should be discontinued and rescue medication started:

- Subjects who have pain and/or photophobia that does not improve, even when there is an improvement in ACC count and/or ACF grade, may be rescued at the discretion of the investigator.
- Subjects who have pain and/or photophobia that worsens may be rescued at the discretion of the investigator.

Initiation of rescue medication is at the discretion of the Investigator. However, it is recommended that the Investigator uses the above guidance to determine when to rescue a subject. If the quantitative ACC count or ACF grade criteria are not met, the Investigator should discuss the qualitative reason(s) for rescue with the Study Medical Monitor for consistency across the study.

9.4.2 Management

Investigators will use clinical judgment to determine when to rescue a subject using the guidance provided in [Section 9.4.1](#) and the appropriate rescue medication to use. All rescued subjects will stop study drug at the time of rescue and will continue in the study through completion of the Visit 6 (POD22) assessments ([Table 1](#)).

If a subject needs to be rescued at Visit 5 (POD15), the Visit 5 (POD15) assessments ([Table 1](#)) should be completed before the subject is administered rescue medication.

Rescued subjects will be considered treatment failures, and the need for rescue medication will not be considered as an AE.

An AE occurring at the time of rescue will be recorded in the eCRF and will be followed by the Investigator to stabilization or resolution of the AE or the end of the study (whichever comes last).

If a subject is rescued, this event will be recorded in the eCRF (not as an AE). Medications used for rescue will be recorded in the ConMeds section of the eCRF, indicating that they were used for rescue.

9.5 Management of Increased IOP

9.5.1 Criteria for Starting IOP-Lowering Medication

Investigators should use the following criteria to determine whether to start IOP-lowering medication:

- After randomization, an IOP > 30 mmHg in the study eye

- After randomization, an IOP ≥ 21 mmHg **AND** an increase of > 10 mmHg from the Visit 2 (POD1) pre-dose baseline in the study eye (both of these criteria must be met)

Initiation of IOP-lowering medication is at the discretion of the Investigator even if neither of the above criteria are met, however, it is recommended that the Investigator uses these criteria to determine when to consider a subject for IOP-lowering medication.

9.5.2 Management

Investigator will use clinical judgment to determine the appropriate IOP-lowering medication to use and when to withdraw study drug and procedures, in consultation with the Study Medical Monitor.

It is important to note that prostaglandin-based IOP lowering medications are prohibited in this study.

- After randomization and start of study drug, if a subject has an IOP > 30 mmHg the Investigator may commence non-prostaglandin-based IOP-lowering medication while continuing the study drug, with appropriate follow-up at the next planned visit or at an unscheduled visit. The subject may require assessment at an unscheduled visit at the investigator's discretion.
 - If the IOP is < 30 mmHg at the next visit, the subject may continue on study drug.
 - If at the next visit, the IOP remains > 30 mmHg while on IOP-lowering medication, then the study drug may be discontinued and alternative IOP-lowering medication may be started, after consultation with the Study Medical Monitor. The subject should continue in the study and complete the assessments indicated in [Table 1](#) through Visit 6 (POD22). The Study Medical Monitor should discuss the persistent elevation of IOP with the Sponsor Medical Monitor.
- After randomization and start of study drug, an IOP of ≥ 21 mmHg **AND** an increase > 10 mmHg from the Visit 2 (POD1)/pre-dose baseline (both criteria must be met) is considered clinically significant and the Investigator should consider starting non-prostaglandin-based IOP-lowering medication while continuing the study drug, with appropriate follow-up at the next planned visit or at an unscheduled visit.
 - If the IOP reduction is satisfactory at the next visit, the subject may continue on study drug.
 - If the IOP reduction of IOP is not satisfactory at the next visit, then the study drug may be discontinued and alternative IOP-lowering medication may be started, after consultation with the Study Medical Monitor. The subject should continue in the study and complete the assessments indicated in [Table 1](#) through Visit 6 (POD22). The Study Medical Monitor should discuss the persistent elevation of IOP with the Sponsor Medical Monitor.

Medications used for treating increased IOP will be recorded in the Concomitant Medications section of the eCRF, noting that they were used to reduce IOP.

10.0 STATISTICAL CONSIDERATIONS

10.1 Statistical Analytical Plan

The Statistical Analysis Plan (SAP) will describe the details of all efficacy and safety analyses and will be finalized prior to database lock.

10.2 Analysis Populations

The analysis populations are defined as follows:

- Intent-to-Treat (ITT) Population: All subjects who are randomized to study drug. Following the ITT principle, subjects will be analyzed according to the treatment they are assigned to at randomization.
- Per-protocol (PP) Population: All subjects in the ITT population who (i) received at least 1 dose of study drug, (ii) do not have major protocol deviations that would impact the evaluation of efficacy and (iii) have at least 80% overall dosing compliance.
- Safety Population: All randomized subjects who receive at least one dose of study drug.

10.3 Statistical Methods

10.3.1 General Approach

All analysis variables will be summarized descriptively by treatment group. Summary statistics for continuous measures will include mean, standard deviation, median, and range. Categorical measures will be summarized by the number and percent of subjects.

10.3.2 Analysis of Efficacy

All efficacy analyses and summaries will be based on assessments in the study eye for each subject.

Subjects who are rescued at any time prior to Visit 5 (POD15) will be considered as treatment failures for the primary efficacy endpoints and the relevant secondary efficacy endpoints. For subjects who discontinue from the study prior to Visit 5 (POD15), the last observation carried forward (LOCF) approach will be used to impute missing data.

For continuous secondary efficacy endpoints, the LOCF approach will also be used to impute the data at visits after subjects are rescued.

The ACC count will be graded as shown below:

Grade	0	1	2	3	4
ACC Count	0 cell	1-5 cells	6-15 cells	16-30 cells	> 30 cells

10.3.2.1 Analyses of Primary Efficacy Endpoints:

The primary efficacy analyses to compare APP13007 against placebo will be conducted on the ITT population using the Pearson Chi-square statistic. Fixed sequence testing will be employed to maintain the 2-sided alpha = 0.05. The primary analyses will first test the difference between treatments in the proportion of subjects with ACC count = 0 (Grade = 0) at POD8 (Visit 4) maintained through POD15 (Visit 5). If the test is statistically significant at the 2-sided alpha = 0.05 level in favor of APP13007, the difference between treatments in the proportion of subjects with Ocular Pain grade = 0 at POD4 (Visit 3) maintained through POD15 (Visit 5) will be tested at the two-sided alpha = 0.05 level.

To confirm the robustness of primary analysis results, sensitivity analyses, including using observed data from all subjects, will be performed. The detailed sensitivity analyses will be described in the SAP.

10.3.2.2 Analyses of Secondary Efficacy Endpoints:

Mean change-from-baseline in ACC Grade, ocular Pain Grade, ACF Grade and visual acuity at PODs 4, 8 and 15 will be analyzed using an analysis of covariance (ANCOVA). The ANCOVA model will include treatment as a fixed effect and baseline as a covariate. The rest of secondary efficacy endpoints will be analyzed using the same method described for the primary efficacy endpoints.

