10.4 Sample Size Estimation

The assumption for the sample size determination was estimated using the Package Inserts of Durezol®, Lotemax® and Inveltys® and results from the APP13007 Phase 2 study (CPN-201). The sample size for ACC count primary efficacy endpoint is based on the assumption of 26% of subjects in APP13007 group with ACC Count = 0 at POD8 and maintained through POD15 and 12% of subjects in matching vehicle placebo group. The two-group chi-square test, with a two-sided significance level of 5% and 92% power, requires 175 subjects per treatment group to detect the difference between APP13007 and placebo.

The same sample size using the assumption of 57% of subjects with Ocular Pain Grade = 0 at POD4 and maintained through POD15 in APP13007 group and 38% of subjects in placebo group will provide 95% power to detect the treatment difference.

With an estimated 5% dropout rate, this study will randomize approximately 185 subjects per treatment group for a total of approximately 370 subjects.

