6.4.3 Handling Dropouts or Missing Data

6.4.3.1 Imputation of Missing Efficacy Data

The missing data handling rule for the study eye will be applied for the efficacy endpoints.

Missing data from subjects who discontinue the study before POD15 assessments without taking rescue medication:

For subjects who prematurely discontinue the study without taking rescue medication, the LOCF approach will be used to impute the missing data. The last observation will be the last assessment value after the first dose of study drug and up to two days following the last dose of study drug.

Missing data from subjects who discontinue the study and take rescue medication before POD15 assessments:

For both categorical and continuous secondary efficacy endpoints of ACC grade, ocular pain grade and ACF grade, subjects who take rescue medication before POD15 assessments and prematurely discontinue the study, the LOCF approach will be used to impute the missing data. The last observation will be the last assessment value after the first dose of study drug and prior to starting rescue medication.

Intermittent missing data:

The likelihood of having intermittent missing data is low. For subjects with intermittent missing data for efficacy endpoints, the LOCF approach will be applied to impute the missing data, i.e., using the data collected from the most recent prior visit after the first dose of study drug.

If no data can be carried forward (i.e., missing assessments at POD 4 visit or no available post-baseline assessments), missing data will be treated as missing for the continuous endpoints and will be considered as 'Non-responder' for the categorical endpoints.

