10.1.2 Primary Analysis

The Pearson's Chi-square test will be used to test the null hypothesis that there is no difference between treatment groups for the primary efficacy endpoints:

1. The proportion of subjects with ACC count = 0 (ACC grade = 0) at POD8, maintained through POD15
2. The proportion of subjects with Ocular Pain grade = 0 at POD4, maintained through POD15

Since the treatment comparisons of the primary efficacy endpoints are in sequential order, the fixed-sequence hierarchical testing approach will be used to adjust for multiple comparisons. The primary analysis will first compare the proportion of subjects with ACC count = 0 (ACC grade = 0) at POD8, maintained through POD15, between APP13007 and placebo. If the test is statistically significant at the 2-sided $\alpha = 0.05$ level in favor of APP13007, the comparison of the proportion of subjects with Ocular Pain grade = 0 at POD4, maintained through POD15, between APP13007 and placebo will be tested at the two-sided $\alpha = 0.05$ level.

Under the hierarchical testing scheme, once the two-sided p-value exceeds 0.05, the endpoint further down in the sequence will not be claimed for statistical significance.

The tabulated summary of the two endpoints will include the Responder (Response =Yes) and Non-responder (Response=No) for ACC count = 0 (ACC grade = 0) at POD8, maintained through POD15, or for Ocular Pain grade = 0 at POD4, maintained through POD15, and the 95% confidence interval (CI) for Responder. The treatment difference of the Responder rates with the associated 95% CI will be presented. The Response will be further categorized as:

Yes (Responder):

- Yes – Without imputed data
- Yes – With imputed data

No (Non-responder):

- No – With Rescue Medication Use
- No – Without Rescue Medication Use
- No – With imputed data

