10.1.3 Sensitivity Analyses

Sensitivity analyses will be performed to confirm the robustness of the primary efficacy analysis results:

1. Analysis of the primary endpoints will be performed using the PP population.
2. “Completed-Case” analysis of the primary endpoints will be performed using the subgroup of Completers based on the ITT population. Completers are defined as the subjects who complete the study and have the data for the ACC count and ocular pain grade assessments at all visits up to POD15.
3. “Observed-Case” analysis of the primary endpoints will be performed using the ITT population and the observed data for subjects who discontinue prior to POD15 without taking rescue medication. The subjects with missing data will be considered as treatment failures (Non-responders).
4. “Worst-Case in the Analysis Window” analysis of the primary endpoints will be performed using the ITT population and using the worst Response at PODs 4, 8 and 15 when multiple efficacy assessments fall within the same analysis window for each Analysis Visit.
5. If more than 5% of data are missing for determining the primary efficacy endpoints in any treatment group, a tipping point analysis will be performed when the statistical significance of a treatment difference between two groups has been claimed for each of the two primary endpoints. Missing data for subjects who take a rescue medication will not be considered as ‘missing’ since the subjects will have been assigned as treatment failures (Non-responders).

The tipping point analysis of the primary endpoints will be performed using the ITT population to determine the number of subjects with imputed data in the placebo group whose response status has to be changed from Non-Responder to Responder in order to make the treatment difference between the two treatment groups no longer statistically significant.

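### Carrying the last value forward lets a non-rescued dropout last seen at zero on POD4 count as a sustained responder, unexamined at POD8 or POD15, even after withdrawal for harm from the drug

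*Protocol*

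**What the plan says.** Both primary endpoints need a zero that lasts: anterior chamber cells (ACC) at zero from POD8 to POD15, and ocular pain at zero from POD4 to POD15.

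For those "who discontinue from the study prior to Visit 5 (POD15), the last observation carried forward (LOCF) approach will be used to impute missing data" (Protocol 10.3.2). SAP 6.4.3.1 repeats the rule: "For subjects who prematurely discontinue the study without taking rescue medication, the LOCF approach will be used to impute the missing data". It adds that the value carried is the last one after the first dose and no later than two days after the last dose. Neither text excepts any reason for leaving.

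The primary results table in SAP 10.1.2 has a responder row labelled "Yes – With imputed data", so imputed responders are intended.

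Two groups are failures by rule: subjects rescued before the POD15 assessment (SAP 6.4.2), and subjects with nothing to carry forward (SAP 6.4.3.1).

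Withdrawal for harm is a separate route. Protocol 9.1.1.3 says: "The investigator may stop the study drug and withdraw the subject if in their opinion the study drug is having a deleterious effect". Protocol 6.3 also turns a subject's own request to stop study drug into withdrawal from the study. Withdrawn subjects are to have the Visit 6 assessments at termination (Protocol 6.2.8).

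SAP 10.1.3 item 3 (Observed-Case) counts missing data as failure, but only as a sensitivity analysis. Item 5, the tipping point, runs only if more than 5% of data are missing and significance has been claimed. It moves vehicle non-responders to responders and nothing else.

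**The concern.** The endpoint is meant to show that clearance, or freedom from pain, lasts to POD15. For a dropout last seen at zero, carry-forward assumes this instead of observing it. The credit is given even when the subject left because the drug was not tolerated, an outcome few would call treatment success.

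The stricter rule is already written into the SAP, so the question is which rule carries the confirmatory claim. The planned stress test does not fill the gap. A tipping point that changes only vehicle non-responders cannot show how far the result depends on APP13007 dropouts credited as responders.

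**Working it through.** **1. Tracing the rule.** SAP Table 3 sets the windows: POD4 = Study Days 2–6, POD8 = Days 7–11, POD15 = Days 12–17. Take a subject with ACC = 0 and pain = 0 on Day 4, last dose on Day 5, withdrawn that day and not rescued.

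| Variation | POD8 and POD15 values | ACC endpoint |
|---|---|---|
| No later eligible value | 0 carried, 0 carried | Responder |
| Day 4 ACC above zero | non-zero carried | Non-responder |
| Rescued | not used | Non-responder |
| Non-zero termination exam within two days of last dose | non-zero | Non-responder |
| No post-dose value | none | Non-responder |

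Pain is scored the same way. The reason for withdrawal appears nowhere in the rule.

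**2. Reproducing the design.** Protocol 10.4 assumes "26% of subjects in APP13007 group with ACC Count = 0 at POD8 and maintained through POD15" and "12% of subjects in matching vehicle placebo group", and states that the test "with a two-sided significance level of 5% and 92% power, requires 175 subjects per treatment group". With pooled variance and no continuity correction:

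n = [1.960·√(2·0.19·0.81) + 1.405·√(0.26·0.74 + 0.12·0.88)]² / 0.14² = 176 (stated 175).

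Approximate power at 175 per arm is 91.9% for ACC and 94.8% for pain at 57% vs 38% (stated 92% and 95%). 175/0.95 rounds up to 185. The stated figures reproduce.

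**3. How many responders are imputed.** Dropouts per arm: 0.05 × 185 = 9.25. The share q last seen at zero is not in the documents. Assuming q = 0.30 (ACC) and 0.60 (pain):
- ACC: 9.25 × 0.30 = 2.8 per arm, or 1.5 points.
- Pain: 9.25 × 0.60 = 5.6 per arm, or 3.0 points.

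**4. Effect on the ACC difference.** With completers at the planned rates p and dropout d, the rate under carry-forward is p(1 − d) + q·d. Setting q = 0 gives non-responder scoring. The unequal dropout splits are assumptions, with q the same in both arms.

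| Dropout APP13007 / vehicle | Failure scoring | LOCF, q = 0.1 | LOCF, q = 0.5 |
|---|---|---|---|
| 5% / 5% | 13.3 points | 13.3 | 13.3 |
| 8% / 2% | 12.2 | 12.8 | 15.2 |
| 2% / 8% | 14.4 | 13.8 | 11.4 |

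Last row, failure scoring: 0.26·0.98 − 0.12·0.92 = 0.1444. At q = 0.5: 0.2648 − 0.1504 = 0.1144. The direction follows the arm that loses more subjects.

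**5. How often the two rules disagree.** 400,000 simulated trials per scenario, 185 per arm, 5% dropout in both arms; q is assumed.

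| Completer rates | q, APP13007 / vehicle | Only LOCF significant | Only failure scoring significant |
|---|---|---|---|
| ACC 26 vs 12 (planned) | 30% / 15% | about 2% | about 1% |
| Pain 57 vs 38 (planned) | 60% / 50% | about 2% | about 1% |
| ACC 22 vs 12 | 30% / 15% | 6.1% | 2.0% |
| Pain 48 vs 38 | 60% / 50% | 7.4% | 3.5% |
| ACC 22 vs 12 | 30% / 30% | 3.2% | 6.5% |

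**6. Could the rule reverse the planned ACC result?** The planned rates give 48 vs 22 of 185 (p < 0.001). Significance is lost at 35 vs 22 (p = 0.061; 36 vs 22 gives p = 0.045). That means reclassifying 48 − 35 = 13 APP13007 responders, more than the 9 or so dropouts expected in the arm.

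**7. Power if dropouts are failures.** Rates become 0.95p on 185 per arm: ACC 24.7% vs 11.4%, pain 54.15% vs 36.1%. Exact power of the Pearson test is 92.2% and 94.3%. At 175 per arm with the planned rates it is 92.5% and 94.6%. At 10% dropout, approximate power is 89.9% and 91.7%.

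**The case against.** The best defence is that carry-forward is even-handed. It carries failures as well as zeros, and with equal dropout and equal last-value shares it leaves the difference unchanged. Non-responder scoring has its own bias: it favours APP13007 if vehicle subjects leave more often. With no true pain effect (38% in both arms), 1% dropout on APP13007, 5% on vehicle and half of dropouts last at zero, false positives in favour of APP13007 are about 5% under failure scoring and about 2% under carry-forward, against a nominal 2.5%. The Observed-Case and completer analyses are prespecified, imputed responders get their own row, and lack of efficacy mostly leads to rescue, which already counts as failure. Protocol 10.6 also words the tipping point more generally than the SAP does.

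Most of this stands. It rules out three stronger readings that a reader might infer:
- That anyone seen only at POD4 and then withdrawn is a responder. The last eligible value must be zero, there must be no rescue, and no later non-zero value may fall within two days of the last dose. The required termination exam can supply such a value.
- That the rule is biased towards APP13007. The documents give neither dropout by arm nor last values, and Protocol 1.4.1.1 reports Phase 2 safety similar to vehicle.
- That a single credited dropout could decide the trial. That is so only at a significance boundary, as for any rule.

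The defence does not justify imputing persistence in an endpoint defined by persistence. Nor does it supply a planned test of credited APP13007 dropouts within the tipping-point analysis, since the SAP's operative version works on vehicle only.

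**Conclusion.** The point holds in this form. A non-rescued subject whose last eligible value is zero at POD4 is a primary responder without examination at POD8 or POD15, whatever the reason for withdrawal. The Observed-Case analysis addresses this, but only as support; the SAP tipping point does not address it on APP13007.

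The size is modest: about 3 (ACC) and 5 to 6 (pain) imputed responders per arm, given 5% dropout and assumed shares at zero of 30% and 60%. At the planned effects the choice of rule seldom changes the conclusion, and with the expected number of dropouts it could not reverse the planned ACC result. It matters mainly if the true effect is smaller or dropout is unequal, and then the direction depends on which arm loses more subjects and on their last values. The case for change rests on what the endpoint claims and on the low cost, not on a demonstrated bias.

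**What to change.** In Protocol 10.3.2 and SAP 6.4.3.1, for the two primary endpoints and sustained flare (ACF) = 0: score as Non-responder any subject who discontinues before POD15 without an observed POD15 value. In SAP 10.1.3, make item 3 the primary rule and keep LOCF as a sensitivity analysis. Run the tipping point in both arms, so that APP13007 dropouts scored as responders are also moved to failure.

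At a minimum, score as failure any subject withdrawn for an adverse event, a deleterious effect or lack of efficacy. The reason for withdrawal is already recorded (Protocol 6.3).

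Costs:
- Responder rates fall by up to about 1.5 (ACC) and 3 (pain) points at 5% dropout on the assumed shares.
- Exact power is 92.2% for ACC (stated 92%) and 94.3% for pain (stated 95%, but already 94.6% at 175 per arm).
- Failure scoring favours APP13007 if vehicle loses more subjects, which is why LOCF and the two-arm tipping point should stay.
- The protocol as well as the SAP must be amended before unmasking, with the IRB approval and FDA submission that Protocol 11.1.3 requires.

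The change covers discontinuation only. A subject who misses POD8 but attends POD15 stays under the intermittent-missing rule in SAP 6.4.3.1, and the amendment should say whether that is intended.
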